4. DATA COLLECTION

4.1 ELECTRONIC DATA CAPTURE (EDC)

MedNet Solutions Incorporated is a privately held company that specializes in web-based clinical data management technology. MedNet will host the EDC system and provide a secure environment that is accessible to authorized individuals through the internet. BIOTRONIK will implement a registry specific configuration using this software to meet the data collection requirements of the protocol. The EDC system is 21 CFR Part 11 compliant and is the platform for electronic case report form (eCRF) data entry, clinical data discrepancy resolution, and access to reports for BIOTRONIK, specified study sites, and any other parties authorized by BIOTRONIK.

4.2 ELECTRONIC CASE REPORT FORMS (eCRFs)

Original data will be collected at each study site and recorded into the EDC system, audited and monitored by BIOTRONIK, via completion of eCRFs. The investigator will be required to use an electronic signature to approve the content of the data reported in the eCRFs.

Information from electronically delivered source data (e.g. programmers) will be captured and stored in a validated environment until the end of the registry.

Subject follow-up is required for all subjects enrolled in this clinical registry. The required follow-up visit dates are based on Plexa lead implant date, and are to be used for the calculation of the dates of the routine follow-up schedule. The following eCRFs will be available in the EDC system:

- Informed Consent
- Enrollment
- Implant
- Lead Values (used for implant lead values and revision lead values)
- Follow-up (3 month \pm 30 days post-implant, 6 months \pm 45 days post-implant, and every 6 months \pm 45 days thereafter for 5 years)
- Adverse Event
- System Revision
- Study Termination
- Protocol Noncompliance

4.3 DATA QUALITY CONTROL

BIOTRONIK will review registry data. At any time, reports may be generated on data completion and missing data for each study site. An EDC system will be used to track received and expected follow-up data and eCRFs for each participant. This system provides the capability to monitor the status, volume, and disposition of data as well as to identify data completed, due, overdue, and backlogged. In addition, all registry data will undergo automatic edit and plausibility checks, which provide information to the study sites to help improve and maintain data quality control procedures, and is designed to detect inaccuracies and inconsistencies.

To ensure protocol compliance at all participating study sites, BIOTRONIK monitors will conduct centralized and / or on-site monitoring throughout the course of the registry.

To ensure compliance with federal regulations, internal policies and procedures, and the registry protocol, the EDC vendor will also be audited by BIOTRONIK or a BIOTRONIK representative during the course of the registry.

4.4 SUBJECT RETENTION

Although the registry sample size has been calculated with a 10% subject attrition rate per year (41% total in 5 years), subject retention in a 5 year registry may pose additional, unforeseen challenges. BIOTRONIK will provide additional tools to the sites in an effort to minimize the number of subjects that are lost to follow-up. The EDC system includes an overview of each subject's follow-up schedule, including the windows for each follow-up.

4.5 SUBJECT DATA CONFIDENTIALITY

All information sent to BIOTRONIK pertaining to each subject will be kept confidential at BIOTRONIK and is subject to FDA inspection. Source documents used to support endpoint adjudication by the CEC in the Plexa Registry will have all confidential subject and site identifiers redacted prior to transmission. Reports submitted to the physician or publications of registry results will not make any reference to subject names.

In order to verify the registry data and ensure registry integrity, monitors from BIOTRONIK, the FDA, and the reviewing Institutional Review Board (IRB) may review and / or copy the registry records

5. RISKS AND RISK MINIMALIZATION

All devices included in this registry are legally marketed and being prescribed by physicians according to FDA approved indications for use. Additionally, all visits in this registry are standard of care. There are no new risks associated with participation in this study. Please refer to the product manuals for risks associated with the implanted leads, ICDs, or CRT-Ds.

6. REGISTRY ORGANIZATION

6.1 SPONSOR

BIOTRONIK is the "sponsor" of the Plexa Registry. A "sponsor" is defined as an entity that initiates, but does not conduct, an investigation. BIOTRONIK's responsibility as the clinical study sponsor is to ensure protocol and regulatory compliance through proper monitoring of the investigation. As the investigator, the physician is responsible for conducting the study in accordance with the signed agreement, the protocol, applicable laws, FDA regulations, and any conditions of approval imposed by the reviewing IRB. The principal investigator must also accept responsibility for all aspects of the study including the actions of any co-investigators participating in the study at the study site.

6.2 CLINICAL EVENTS COMMITTEE

A Clinical Events Committee (CEC) consisting of at least 3 independent electrophysiologists will review and adjudicate adverse events that occur during the registry. The CEC will be blinded to the clinical registry site and subject identity, and to minimize bias, members will not participate as investigators. The CEC will create a registry specific charter defining the adverse event adjudication process, specifically detailing review guidelines along with appropriate response timelines.

All protocol defined adverse events included in the primary and secondary endpoint analysis (see Section 9.3.1 and Section 9.3.2) will be adjudicated by the CEC. The CEC will indicate whether the adverse event is related, possibly related, not related, or has an unknown relation to the Plexa lead. The CEC will have the responsibility to adjudicate the classification of each reported adverse event as implant procedure, implanted pulse generator, lead, or non-procedure non-system related, to adjudicate the category of AE (e.g. Plexa lead dislodgement, major hematoma, etc.), and to assess the seriousness of each AE.

7. REGISTRY MONITORING

7.1 SUMMARY

BIOTRONIK's responsibility as the clinical registry sponsor is to ensure protocol and regulatory compliance through proper monitoring of the investigation. BIOTRONIK requires IRB review and a subject Informed Consent Form for all after-market research. Monitoring may be conducted on-site at the study site or remotely by BIOTRONIK monitors.

Through on-site or centralized monitoring, BIOTRONIK will assess the site's performance in the following areas:

- Verification that informed consent was obtained
- Adherence to protocol eligibility criteria and requirements
- Conduct and documentation of procedures and assessments related to:
 - Study endpoints
 - Protocol required safety assessments
 - Evaluating, documenting, and reporting AEs, subject deaths, and withdrawals, especially when a withdrawal may be related to an adverse event.
- Investigator oversight and delegation of authority to study personnel
- Verification of study-specific required documentation
- Conduct and documentation of procedures essential to trial integrity
- Adherence to the applicable FDA regulations regarding the obligations of the investigator and maintenance of records.

As the investigator, the physician is responsible for conducting the registry in accordance with the signed agreement, the protocol, applicable laws, FDA regulations, and any conditions of approval imposed by the reviewing IRB. The principal investigator must also accept responsibility for all aspects of the registry including the actions of any sub-investigators participating in the registry at the study site.

7.3 ON-SITE MONITORING VISITS

A monitor will conduct monitoring visits at study sites in accordance with the Monitoring Plan. Sites are required to support these visits and the study monitoring effort. On-site monitoring visits will also provide an assessment of the continued acceptability of the facilities to continue participation in the registry.

7.4 CENTRALIZED MONITORING

Centralized monitoring will be conducted throughout the course of the study in accordance with the Monitoring Plan. Some examples of data that may be monitored remotely include un-redacted, signed informed consent forms, enrollment, implant information, device data, adverse events reported in the EDC system, etc. Sites are required to support centralized monitoring by providing source documents to BIOTRONIK in order to source data verify data reported in the EDC system and resolving queries in a timely manner.

8. REGISTRY COMPLETION

BIOTRONIK will notify the registry site upon completion or termination of the registry or investigator's participation in the registry. At BIOTRONIK's request, an investigator will return any pertinent information in their possession. Whenever possible, BIOTRONIK will provide a final report to each study site that has closed since the previous report. Upon termination of this registry, BIOTRONIK personnel may conduct a registry closure visit according to the Monitoring Plan. If a closure visit occurs, during the visit, BIOTRONIK will verify registry records and ensure that the investigator understands any applicable regulatory requirements including those related to record retention. The investigator must retain records related to the registry for a period of 2 years after the registry is completed.

In the event that the registry is suspended or terminated, the investigator must inform all enrolled subjects who at that time have not yet exited the registry. Standard patient care will be ensured by the study site.

9. ADVERSE EVENTS

An adverse event (AE) is defined as any unfavorable and unintended event that occurs during the course of the study. The investigator will be required to assess and classify each reported adverse event as related to either the implant procedure, implanted pulse generator, Plexa lead, RV lead (separate from Plexa lead), right atrial lead, left ventricular lead, or as non-procedure non-system related. All reportable adverse events occurring after informed consent are collected. Reportable adverse events occurring prior to consent will only be collected beginning from the date of implant of the study system (the Plexa system active at the time of enrollment).

The study site should report each adverse event via an Adverse Event eCRF and if the IRB is notified, provide a copy of the IRB adverse event notification to BIOTRONIK.

9.1 REPORTABLE ADVERSE EVENTS

The following AEs (sorted by classification) will be reported if they meet the definition of a primary or secondary endpoint as defined in Section 9.3. The classifications listed below are general classifications for site reporting purposes. Detailed information for some classifications is located in Appendix A. The CEC charter may include alternate classifications for some adverse events.

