9.4 ADVERSE EVENT REPORTING

The adverse events that an IRB considers reportable are dependent on the particular IRB. To avoid underreporting, BIOTRONIK recommends that, at a minimum, the investigator reports the Plexa lead-related adverse events that occur during the Plexa Registry to BIOTRONIK and the IRB.

The registry site will report the adverse event on the Adverse Event eCRF. Additionally, registry sites may report adverse events through MedWatch, FDA's adverse event reporting tool for market-released devices. As defined in BIOTRONIK's internal procedures, these adverse events may be reported by BIOTRONIK through manufacturer's MedWatch reports.

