11.2 INVESTIGATOR REPORTS

Investigators are required to prepare and submit to BIOTRONIK the following complete, accurate, and timely reports on this investigation when necessary:

- Notification of a subject death during the registry
- Notification of the withdrawal of IRB approval
- Annual progress reports prepared for the IRB
- Notification of any deviations from the registry plan
- Notification that an informed consent was not obtained from the subject
- Final summary report prepared for the IRB
- Any other information upon the request of an IRB, the FDA, or BIOTRONIK

Table 6 outlines the responsibilities, including time constraints, for submitting the above reports.

Table 6: Investigator Reporting Responsibilities

Type of Report	Report to BIOTRONIK	Report to IRB	Time Constraints of Notification
Subject Death During Registry	Required	Required	BIOTRONIK as soon as possible and as required by reviewing IRB
Adverse Event	Required	IRB dependent	Within 10 calendar days after notification of the event
Subject Withdrawal	Required	Required	BIOTRONIK as soon as possible and as required by reviewing IRB.
Withdrawal of IRB Approval	Required	N/A	Within 5 working days
Progress Report	Required	Required	Submitted not less often than yearly
Significant Deviations from Registry Plan	Required	Required	Within 5 working days after emergency to protect life or physical well-being of subject, otherwise prior approval by BIOTRONIK is required
Informed Consent Not Obtained	Required	Required	As soon as possible after discovery and no more than 5 working days

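### Section 9.1 has sites apply the endpoint definition before reporting, so a Plexa lead event managed without surgery that a site misjudges never reaches the Clinical Events Committee

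*Combined protocol and SAP*

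**What the plan says.** All references are to the combined protocol and SAP.

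- **Section 9.1** lists event types and says they "will be reported if they meet the definition of a primary or secondary endpoint as defined in Section 9.3". The condition covers primary and secondary endpoints.
- **Section 9.3.1** counts a Plexa lead event in the primary endpoint if surgery on the lead was needed, if a Plexa lead event led to death, or if one of three non-invasive actions was taken. Those are a polarity or mode change made because of a mechanical or electrical integrity problem, switching the lead off for that reason, and a medical decision to keep using a lead with a recognised performance issue. Other problems solved by reprogramming are declared not to be adverse events.
- **Section 9.3.2** takes a Plexa lead event into secondary endpoint 4 only if 9.3.1 excluded it. The exclusions are dislodgement, high threshold or capture failure within 30 days of implant or lead revision.
- **Section 6.2** sends the CEC "All protocol defined adverse events included in the primary and secondary endpoint analysis". It also has the CEC decide the classification and category of each event that is reported.
- **Section 9.2** counts only events adjudicated as related. Possibly related, not related and unknown do not count.

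Reporting is also described elsewhere. Section 9 defines an event broadly ("An adverse event (AE) is defined as any unfavorable and unintended event that occurs during the course of the study"), says "All reportable adverse events occurring after informed consent are collected", and then says "The study site should report each adverse event via an Adverse Event eCRF". Section 9.4 recommends that, "at a minimum, the investigator reports the Plexa lead-related adverse events that occur during the Plexa Registry to BIOTRONIK and the IRB". Table 6 in Section 11.2 makes adverse event reports to the sponsor required, "Within 10 calendar days after notification of the event", with no endpoint condition.

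**The concern.** Independent adjudication is meant to take site judgment out of the primary endpoint. Under 9.1 the site's judgment comes first, and for one group of events it is final. If a site changes the polarity of a Plexa lead, or continues with a lead that shows noise, and decides that 9.3.1 is not met, 9.1 gives it no reason to file a form. The issue is misjudgment of events that do meet the definition; the definition itself is not in question.

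A missed subject who completes five years is counted as event-free. The error therefore runs toward meeting the 92.5% goal. Differing reporting instructions add a second problem: sites may apply different thresholds, and the registry would not know which.

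**Working it through.** **1. Which events can be lost**

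| Event, as the site sees it | Reported under 9.1? | Can the CEC make it primary? |
|---|---|---|
| Plexa lead event with lead surgery | Yes, primary or secondary | Yes |
| Major procedure event, or generator event with invasive intervention | Yes, secondary endpoint 4 | Yes, by reclassification (6.2) |
| Early Plexa dislodgement or threshold/capture event with a listed action | Yes, secondary endpoint 4 | It is seen, but excluded by 9.3.1 |
| Other Plexa lead event without surgery, judged to meet 9.3.1 | Yes, primary | Yes |
| Other Plexa lead event without surgery, judged not to meet 9.3.1 | No | No; it is never seen |

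The last row is the main gap. Those events have no route through 9.3.2, so they are either primary or unreported.

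The event types concerned are not rare. Table 1 (GALAXY) lists 21 noise or oversensing events, 16 low-impedance and 15 high-impedance events: 21 + 16 + 15 = 52 of 64 primary events. The documents do not say how these were managed, so this shows relevance and not a missed-event rate.

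**2. Reporting thresholds side by side**

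| Section | What is to be reported or recorded |
|---|---|
| 9.1 | Listed events that meet a 9.3 endpoint definition |
| 9 | Reportable events, and also each adverse event |
| 9.4 | Plexa lead-related events as a minimum, worded as a recommendation |
| 11.2, Table 6 | Adverse events, required, no endpoint condition |
| 3.2.6 | Any lead, generator or procedure event at a system revision |
| 3.2.4 | Study-defined events at routine follow-up |

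**3. The plan's own figure**

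Inputs from Section 2.3: exact binomial test, one-sided alpha 0.025, goal 92.5%, expected rate 95.0%, 750 evaluable subjects, 10% attrition per year.

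- The exact lower 95% bound exceeds 92.5% with 42 event subjects (708/750 event-free, bound 92.51%) but not with 43 (bound 92.35%). The limit is 42.
- Alpha: P(X ≤ 42 | 750, 0.075) = 0.0247.
- Power: P(X ≤ 42 | 750, 0.05) = 0.801.
- Enrolment: 750 / 0.9^5 = 1270.1, rounded up to 1271.

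The stated sample size is reproduced.

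**4. Effect of missed events**

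Let f be the share of subjects with a qualifying event whose event is never reported. This is assumed; the documents give no value. Take the true rate at the limit, 7.5%, so that 750 × 0.075 = 56.25 event subjects are expected. Treat missed subjects as event-free with n fixed at 750, and ignore CEC reclassification in either direction. Then P(pass) = P(X ≤ 42 | 750, 0.075 × (1 − f)).

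| f | Observed rate | Subjects missed (56.25 × f) | P(pass) |
|---|---|---|---|
| 0 | 7.5% | 0 | 2.5% |
| 2% | 7.35% | 1.1 | 3.5% |
| 5% | 7.125% | 2.8 | 5.6% |
| 10% | 6.75% | 5.6 | 11.7% |

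Because f applies to all qualifying events, it must be read against the exposed subset. The documents give no split between invasive and non-invasive management. If 20% were non-invasive (assumed) and sites missed 10% of those, f = 0.20 × 0.10 = 2%. Reaching f = 10% would require sites to miss half of them.

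**The case against.** A reader might infer that the CEC can remove primary events but never add one. The documents do not support that. Section 9.1 also admits secondary-endpoint events, and 6.2 lets the CEC reclassify each reported event. A perforation that the site called procedure-related, or a surgically treated generator failure, can be moved into the primary endpoint.

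The exposed group is also limited. Surgical events mostly qualify as primary or secondary wherever the site attributes them. Section 3.2.6 requires a revision record even when the Plexa lead is not directly affected, and 10.2.2 asks whether a death was related to the lead.

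Nor do the other sections make sponsor reporting merely optional. The recommendation in 9.4 follows a remark on differing IRB rules, the next paragraph says that the site will complete the form, and Table 6 makes sponsor reports required. The sentence in Section 9 about each event can be read as describing how to report, since it follows two sentences on reportable events.

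There are safeguards: monitors assess event reporting (7.1) and verify source data (7.4), and interrogations and Home Monitoring pages are stored (3.2.4). The CEC charter and Monitoring Plan are not among the documents and may add a submission rule.

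These points narrow the concern but do not remove it. A site that withholds an event it judged non-qualifying has followed 9.1, so a monitor checking adherence may find nothing wrong. Interim visits need not be entered as visits in the EDC (3.2.5), so a non-surgical response at such a visit may leave no visit record there. Stored device data help only if someone reviews them for unreported events, and no section shown assigns that review.

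**Conclusion.** The point holds as a reporting gap for Plexa lead events managed without surgery, together with reporting thresholds that need reconciling. The direction is clear: unreported qualifying events raise the event-free rate and favour passing. The size is not known. On assumed missed shares of 2% to 10% of all qualifying events, the chance that a lead at the 7.5% limit passes rises from 2.5% to between 3.5% and 11.7%. The lower end is more plausible if non-surgical events are a small part of the total. The sample size and the endpoint definition are not at fault. The change is worth making because a few subjects matter at this limit and the remedy is mostly wording.

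**What to change.** 1. **Sections 9.1 and 9.4:** require sites to report to the sponsor every event type in 9.1.3 that possibly involves the Plexa lead and that led to surgery, polarity or mode reprogramming, the lead being programmed off, or a documented decision to continue its use, whether or not the site believes 9.3.1 is met.
2. **Sections 6.2 and 9.2:** send all of these to the CEC, and state that the CEC, not the site, applies 9.3.1.
3. **Sections 3.2.4, 9.3.1 and 9.3.2, and the Appendix A definitions of capture failure, undersensing and high threshold:** reword so that they say what counts in the analysis, not what is reported. Otherwise sites could still apply the filter.
4. **Sections 3.2.6, 9 and 11.2 (Table 6):** refer to the same single reporting rule.
5. Keep the 9.3 filter for generator, procedure and other-lead events.

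Nothing changes in the endpoint definition, the sample size or clinical care. The cost is additional adverse event forms and CEC adjudications. Their volume is unknown, because the documents give no count of non-qualifying lead events. For scale only, GALAXY's 109 primary or secondary lead events in 1997 subjects correspond to 109 / 1997 × 1271 ≈ 69 events in this registry. Reports of events judged non-qualifying would come on top of a number of that order.

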9.1.1 Implant Procedure-Related Adverse Events

An AE will be classified as procedure-related if any one of the following occurred as a result of the implant procedure:

- Arrhythmias associated with the implant procedure
- Cardiac perforation with or without tamponade
- Coronary sinus dissection
- Damage to lead during procedure (e.g. accidental cut to lead body during pocket revision, device replacement, etc.)
- Incorrect lead connection with pulse generator
- Lead dislodgement during a procedure (e.g. during pocket revision, device replacement, etc.)
- Loose set-screw
- Major hematoma
- Non-healing pocket dehiscence requiring intervention
- Pneumothorax associated with the implant procedure
- Primary infection
- Pulmonary embolism associated with the implant procedure
- Venous occlusion associated with the implant procedure
- Other major implant procedure related adverse event

